### **7.6.4 Years 2 and 4**

The following assessments will be conducted by telephone or office visit at years 2 and 4 (+ 45 days):

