## 8 ADVERSE EVENTS

### 8.1 Adverse Event Definitions

An **Adverse Event** (AE) is any untoward medical occurrence, unintended disease or injury or untoward clinical signs (including abnormal laboratory findings) in subjects, users or other persons, whether or not related to the study device. For users or other persons, this definition is restricted to events related to the study device.

AEs may be volunteered by subjects, elicited or collected via observation by the Investigator or designee, or discovered by review of clinical records by Edwards Safety team or Edwards Monitoring team. Subjects will be instructed to contact the Investigator and/or study coordinator if any significant AEs occur between study visits.

A **Serious Adverse Event** (SAE) is any adverse event that:

- Led to death;
- Led to serious deterioration in the health of the subject that either resulted in:
  - a life-threatening illness or injury;
  - a permanent impairment of a body structure or a body function;
  - in-patient or prolonged hospitalization;
  - medical or surgical intervention to prevent life-threatening illness or injury or permanent impairment to body structure or a body function;
- Led to fetal distress, fetal death or congenital abnormality or birth defect;
- Significant medical event: Important medical events that do not meet the above criteria may still be considered an SAE if they seriously jeopardize the subject and require immediate medical or surgical intervention to prevent one of the aforementioned outcomes.

**NOTE 1:** Planned hospitalization for pre-existing condition, or a procedure required by the Clinical Investigation Plan, without a serious deterioration in health, is not considered a serious adverse event.

**NOTE 2:** Permanent impairment of a body structure or a body function - An AE, which results in a substantial disruption of a person's ability to conduct normal life functions. This does not pertain to minor events, but to serious events which result in a significant, persistent or permanent change, impairment, damage or disruption in the subject's body function/structure, physical activities and/or quality of life.

**NOTE 3:** Life-threatening – an event in which the subject was at risk of death at the time of the event; it does not refer to an event which hypothetically might have caused death if it were more severe.

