## **8.2      Investigator Assessment of AEs**

For each AE, the Investigator will determine whether the event is related to the device and/or the implant procedure, whether it was anticipated or not anticipated (based on the list of potential risks provided in the IFU) and whether the event meets the definition of an SAE or USADE.

The causal relationship of the event to the device and the implant procedure will be categorized as follows:

- 1) Not related: relationship to the device or procedures can be excluded when there is no temporal relationship, the event is not a known adverse effect of similar devices or procedures, it is not clinically plausible, or the event can be attributed to another cause.
- 2) Unlikely: the relationship with the use of the device seems not relevant and/or the event can be reasonably explained by another cause, but additional information may be obtained.
- 3) Possible: the relationship with the use of the device is weak but cannot be ruled out completely. Alternative causes are also possible (e.g. an underlying or concurrent illness/ clinical condition or/and an effect of another device, drug or treatment). Cases where relatedness cannot be assessed or no information has been obtained should also be classified as possible.
- 4) Probable: the relationship with the use of the device seems relevant and/or the event cannot

be reasonably explained by another cause, but additional information may be obtained.

5) Causal relationship: the event is associated with the device or with procedures beyond reasonable doubt when there is a temporal relationship, the event is a known adverse effect of similar devices or procedures, it is clinically plausible, or the event cannot be attributed to another cause.

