### 8.3 AE Reporting Requirements

All AEs will be captured from the time of enrollment until subject participation has ended (i.e. completion of study or discontinuation). See section 8.3.1 for events that are not required to be reported to Edwards.

Pre-existing medical conditions or symptoms reported prior to subject enrollment will not be recorded as an AE. In the event there is a worsening in the pre-existing medical condition or symptoms due to the device or study-related procedure, then an AE must be recorded.

Death should not be recorded as an AE, but should be reflected as an outcome to another specific AE.

If known, the diagnosis for an AE should be recorded, rather than listing individual signs and symptoms.

All AEs will be reported in subject medical records, and the appropriate eCRF throughout the duration of the study, and will be followed until resolution, stabilization or study completion.

All SAEs and Device Deficiencies that might have led to a SAE should be reported to Edwards immediately, but not later than 3 calendar days after site study personnel's awareness of the event.

Other AEs must be reported to Edwards as soon as practical but no later than 10 working days of awareness.

Information must be entered into the electronic database or, when the electronic database is not available, reported directly to the Edwards Safety Officer. In the event that the EDC system is not in service, a paper copy of the AE CRF must be e-mailed to [contact] according to the timelines described above.

At the time of initial AE notification, the following minimal information must be provided:

- Subject ID
- AE term/diagnosis
- AE onset date

For selected events, the site might be requested to provide to Edwards (or designee) a copy of

anonymized supporting documentation (such as hospital record, laboratory results, autopsy results).

All AEs will be reviewed by the Edwards Safety Officer. Each AE will be assessed as to its relationship to the study device and/or implant procedure, whether it was anticipated or not anticipated, and whether it qualifies as an SAE and USADE.

Depending on the local requirements or following agreement between both parties, Edwards or the Principal Investigator will be responsible for performing safety reporting to the EC according to the relevant local regulatory requirements.

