### 10.3 Statistical Analyses

Descriptive statistics will include: number of subjects and frequencies in % for categorical variables and mean and standard deviation for continuous variables. Kaplan-Meier estimates will be calculated for survival outcomes and where appropriate for adverse event outcomes.

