Pulmonary Hypertension	
Pulmonary hypertension (PH), defined as a mean pulmonary arterial pressure <math>\geq</math> 25 mmHg at rest in the presence of Left Atrial Pressure(LAP)/Wedge pressure <math>\leq</math> 15 mmHg and is often characterized by a progressive and sustained increase in pulmonary vascular resistance that eventually may lead to right ventricular (RV) failure
	ACC/Sponsor										
Pre-existing Condition	
A pre-existing condition is any chronic, recurring condition identified prior to enrollment in a clinical study, whether present at enrollment or not. A preexisting condition is not an adverse event unless it worsens as a result of the study treatment.
	Sponsor										

Term	Definition	Reference/ Justification
Reintervention	
Any intervention that repairs, alters or replaces a previously implanted or operated valve, which occurs after the completion of the valve implant procedure and the transfer to the procedure room. These interventions include:
 
 
• Balloon aortic valvuloplasty
 
• Surgical aortic valve replacement
 
• Valve in valve
 
• Paravalvular leak closure
 
	STS/AATS
Stroke / Transient Ischemic Attack (TIA)	
Diagnostic Criteria
 
Acute episode of a focal or global neurological deficit with at least one of the following:
 
 
• change in level of consciousness
 
• hemiplegia, hemiparesis, numbness or sensory loss affecting one side of the body
 
• dysphasia or aphasia, hemianopia, amaurosis fugax, or other neurological signs or symptoms consistent with stroke
 
 
AND
 
No other readily identifiable nonstroke cause for the clinical presentation (e.g., brain tumor, trauma, infection, hypoglycemia, peripheral lesion, pharmacological influences) to be determined by or in conjunction with designated neurologist
	VARC-2

Term	Definition	Reference/ Justification

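### Appendix B counts worsening of a pre-existing condition as an adverse event only if study treatment caused it, which contradicts the causality-free definition in Section 8.1 and pre-empts the relatedness step in Section 8.2

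*Combined protocol and SAP*

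**What the plan says.** Four places in the combined protocol and SAP bear on whether worsening of a known condition is an AE.

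- **Appendix B, Pre-existing Condition.** The entry covers chronic, recurring conditions identified before enrollment, and says: "A preexisting condition is not an adverse event unless it worsens as a result of the study treatment".
- **Section 8.3.** Conditions or symptoms reported before enrollment are not recorded as AEs. The exception is a "worsening in the pre-existing medical condition or symptoms due to the device or study-related procedure, then an AE must be recorded". Nothing is said about worsening from any other cause.
- **Section 8.1.** An AE is any untoward medical occurrence in subjects, "whether or not related to the study device". NOTE 1 says that a planned admission for a pre-existing condition, "without a serious deterioration in health, is not considered a serious adverse event".
- **Section 8.2.** "For each AE, the Investigator will determine whether the event is related to the device and/or the implant procedure". The five grades include not related and unlikely, and cases that cannot be assessed go to possible.

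Section 8.3 adds a rule on deaths: "Death should not be recorded as an AE, but should be reflected as an outcome to another specific AE". For analysis, Section 10.3 plans descriptive statistics and says: "Kaplan-Meier estimates will be calculated for survival outcomes and where appropriate for adverse event outcomes".

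**The concern.** Section 8.1 makes AE status independent of cause. Appendix B makes it depend on cause for one class of event. Both are current text, so a site following Appendix B and a site following Section 8.1 would record the same event differently.

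That class of event is foreseeable here. Every subject enters with severe aortic stenosis and NYHA class II or higher, and follow-up runs to five years.

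Two things are at stake. First, the descriptive AE rates, and any Kaplan-Meier AE estimates, would be understated and would depend on each site's opinion about cause. Second, a serious worsening judged unrelated could stay outside the 3-calendar-day SAE report and would not reach the sponsor's safety officer, whose review covers AEs only. The site's causal judgement would then go unchecked, although Section 8.3 provides a second assessment.

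**Working it through.** The plan gives no figure to reproduce on this point. The check compares the text and counts entries in the visit schedule.

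**One event under each rule.** Take a subject with known heart failure that worsens in year 2, for a reason the investigator considers unrelated to the device or the procedure.

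| Rule | Result |
|---|---|
| Section 8.1 | AE, because cause is irrelevant to the definition |
| Section 8.2 | Graded not related or unlikely, after it has been recorded |
| Section 8.3 | Recording not required; the text is silent on unrelated worsening |
| Appendix B | Not an AE |

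The first and last rows cannot both be followed.

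**Order of judgement.** Section 8.2 takes events that are already AEs and grades them. Appendix B needs the causal answer before the event can be an AE. For worsened chronic conditions this leaves the not related and unlikely grades with nothing to grade. The default to possible is not a dependable rescue, because it too applies to events already classed as AEs.

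**Seriousness.** Section 8.1 defines an SAE as an AE meeting further criteria. If the event is not an AE, it cannot be an SAE.

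**Other text that might settle it.** Section 8.3.1 exempts named expected events and pre-planned surgery, and does not mention worsening of chronic disease. The repeat-hospitalization entry in Appendix B points the other way: a planned admission for a pre-existing condition counts if the baseline condition has worsened, with no test of cause.

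**Direction.** Let R be the related AEs, U the unrelated new-onset AEs, and W the unrelated worsenings of pre-existing conditions.

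- Count under Section 8.1: R + U + W
- Count under Appendix B: R + U
- Difference: W, which is zero or more, so AE counts can only fall or stay the same
- Related share: R/(R + U) under Appendix B is at least R/(R + U + W) under Section 8.1, so this share can only rise or stay the same

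In a time-to-first-event analysis, a subject whose only event is dropped moves from event to censored, which lowers the Kaplan-Meier estimate of incidence. If that subject has a later recorded event, the first event is delayed rather than lost.

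**What else is collected.** Table 3 and Sections 7.6.1 to 7.6.4 schedule 7 visits after discharge: 30 days, 6 months, and years 1, 2, 3, 4 and 5.

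| Item | Visits | Count |
|---|---|---|
| AEs | all | 7 of 7 |
| NYHA class | 30 days, years 1, 3, 5 | 4 of 7 |
| Weight, blood pressure, heart rate | 30 days, years 1, 3, 5 | 4 of 7 |
| TTE | 30 days | 1 of 7 |
| Creatinine | none (last at discharge) | 0 of 7 |
| AEs and antithrombotics only | 6 months, years 2, 4 | 3 of 7 |

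Those last three visits may also be done remotely; for two of them Section 7.6.4 says: "The following assessments will be conducted by telephone or office visit at years 2 and 4".

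**The case against.** The strongest reply is that the explicit exclusion is one glossary sentence. Section 8.3 only says when an AE must be recorded, and it also says that all AEs are captured, so Section 8.1 could govern where it is silent. Alternatively, Appendix B could be a deliberate sponsor carve-out, as Section 8.3.1 is. Neither reading removes the problem. The Appendix B wording is exclusive, and no text says which rule prevails. If it is a carve-out, under-recording becomes the working rule. Section 8.3.1 also differs in kind: it waives reporting of listed events, whereas Appendix B denies AE status.

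Several narrower objections stand:

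- The conflict with Section 8.2 is one of order, not of opposing sentences.
- NOTE 1 in Section 8.1 concerns planned admissions and gives only indirect support.
- Deaths would not be lost. All-cause mortality is defined without a relatedness filter, survival is analysed separately, and an exit form records the reason for discontinuation. The gap is that a death from excluded worsening has no AE to be the outcome of.
- There are real safeguards. The Appendix B definitions of acute kidney injury, heart failure, myocardial infarction, cardiac arrest and atrial fibrillation carry no study-treatment test. All overt bleeding after the procedure must be reported. Sponsor safety and monitoring staff review records. Many serious worsenings could surface by these routes.
- The visit counts show how little else is collected late in follow-up. They do not measure the bias.

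**Conclusion.** The concern holds. Appendix B is wrong as written, and correcting it alone would leave the causal condition in Section 8.3.

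The error lowers AE counts. Its size cannot be estimated, because the documents give neither the expected frequency of worsening nor the share that would be judged unrelated. The conclusion assumes only that some sites would apply Appendix B literally.

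The reach is limited to chronic, recurring conditions identified before enrollment. Procedural success, major vascular complications, valve migration or embolization, the 90% criterion and new-onset events are untouched. AE analysis is descriptive and there is no comparator. It should be corrected because it can divert serious events from SAE reporting and from the sponsor's relatedness review, but it does not threaten the primary result.

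**What to change.** Make two edits so that recording does not depend on cause:

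1. **Section 8.3:** delete the phrase limiting the recording of worsening to that due to the device or a study-related procedure.
2. **Appendix B, Pre-existing Condition:** replace the closing condition on study treatment with *in severity or frequency, regardless of cause*.

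Relatedness is then assigned under Section 8.2 after the event is recorded. The severity-or-frequency wording is a drafting choice; deleting the causal phrase in Appendix B, or referring there to Section 8.1, would also remove the definitional conflict. Section 8.3 should be edited in either case so that the two places agree.

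The cost is a written amendment under Section 12.6: submission to the ethics committee and regulatory agencies as applicable, IRB/EC approval at each of up to 8 sites, any required training, and written sponsor approval. It can be bundled with another amendment. Sites will enter more AEs and reported AE rates will be higher. The edits concern event recording only and change no clinical rule.
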